Leveraging the Depression And Primary-care Partnership for Effectiveness-implementation Research (DAPPER) – will be initially randomized to 12 weekly one-hour sessions of IPT (3 months) or 6 months of fluoxetine (tapering up to 60mg). Those participants who are not in remission with at the conclusion of initial treatment will be re-randomized to second-line treatment (see below). Prior to randomization, participants will be given the option to receive their treatment at the health facility or by telephone.

Participants who are randomized to fluoxetine and conduct their visits by telephone will need to collect their medication at the health facility. If participants do not collect their medication at the health facility, fluoxetine may be delivered to participants in the community. A smaller, Part 2, of the study will consist of qualitative interviews and focus groups to assess the overall implementation strategy and gather feedback on the specific interventions. Please see "Part 2," below (and additional consent for this aspect of the study, attached).

Randomization and blinding: Randomization will take place after baseline measures are complete. Randomization will be done in blocks of 10 and stratified by sex and telephone vs in-person treatment to ensure that the treatment groups are approximately equal in size and in gender distribution and telephone vs in-person treatment. See below

for second randomization information. Clinical evaluators who conduct follow-up assessments will be blinded to treatment assignment. Participants, IPT therapists, fluoxetine providers cannot be blinded because they will either be providing or receiving the IPT and/or Fluoxetine treatment and therefore they will know their treatment status. In addition, at least one study coordinator will not be blinded to assist with tracking of participants.

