Study visits: To characterize the trajectory of symptom change during treatment, participants will be re-evaluated at the mid-point of treatment (month 1.5 for IPT and month 3 for fluoxetine). Treatment mid-point data is valuable because it can inform the minimum duration of treatment necessary to optimize mental health gains in a setting of scarce mental health resources. For example, if 90% of all observed treatment gains are achieved in the first half of treatment, subsequent implementation efforts might consider shortened courses of treatment. Participants will be assessed at month 3 (end of IPT treatment, mid-point of fluoxetine treatment) and at month 6 (end of fluoxetine treatment). For those participants who are in remission from depression and/or PTSD, follow up assessments will then continue at 9 month, 12 month and then at six month intervals until month 30 to assess for maintenance of gains and relapse. Assessments may be done at the health facility or by telephone. We are defining remission as absence of disease as defined by threshold criteria for Diagnostic and Statistical Manual of Mental Disorders-V (DSM-V) for PTSD and MDD. Those participants who have not yet remitted will be re-randomized to: switch of treatment (from IPT to fluoxetine or vice versa) or combination treatment (addition of IPT to fluoxetine or vice versa). See Figure 3.

Assessment schedule and rationale:

In order to characterize the trajectory of symptom change during treatment, participants will be re-evaluated at the mid-point of treatment (month 1.5 for IPT and month 3 for fluoxetine). Treatment mid-point data is valuable because it can inform the minimum duration of treatment necessary to optimize mental health gains in a setting of scarce mental health resources. For example, if 90% of all observed treatment gains are achieved by month 1.5, subsequent implementation efforts might consider shortened courses of treatment. Participants will be assessed at end of treatment (month 3 for IPT and month 6 for fluoxetine) and fluoxetine recipients will be tapered off the medication. At six months, participants will be re-assessed and then monitored at 6-month intervals until month 30 (Figure 3). Assessment visits may be done at the health facility or over the telephone.

Measures (Table 1): *Demographics.* We will obtain usual demographic measures, education, including individual income, assets, education and school fees, healthcare utilization, and time allocation.

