therapist (see therapist selection and training procedures, above), in 12 weekly 60-minute sessions. Participants randomized to receive fluoxetine will meet or speak with fluoxetine trained provider at baseline, 2 weeks, 4 weeks, 2, 3, 4, 5, and 6 months, for a total of eight appointments. Participants will be assessed for initiation of fluoxetine and advisement on common side effects. Fluoxetine participants will be started on 20mg (1 capsule per day) and will return for assessment of initial efficacy/tolerability at week 2. If the participant does not have any prohibitive side effects, dose will be maintained at 20mg (1 capsule). Participant will return for re-assessment at week 4, if the participant does not have any prohibitive side effects and does not have improvement on the Patient Health Questionnaire-2 (PHQ-2), dose will be increased to 40mg (2 capsule). At month 2, if the participant does not have any prohibitive side effects and does not have improvement on the PHQ-2, the dose will be increased to 60mg (3 capsule). Participants receiving treatment by telephone may be able to receive a 3 month supply at the minimum dose (20 mg per day). If the dose is increased during the intervening treatment visits, the participant will need to receive additional medication. Participants receiving treatment by telephone will be asked to pick up their medication within two days of their treatment call. If they do not collect their medication within 2 days, the medication will be delivered in the community. Studies support that higher fluoxetine doses do not show additional benefit.(Jakubovski, Varigonda, Freemantle, Taylor, & Bloch, 2016) See Protection of Human Subjects section for details on fluoxetine side effect management. The participant will be maintained at 20, 40 or 60 mg at the month 3, 4, and 5 visits, if the participant does not have any prohibitive side effects. At the month 6 visit, participants will be given instructions for tapering off fluoxetine, with decrease of the dose by 20mg

increments each week until reaching zero. Participants who were maintained on 20 mgs throughout the treatment period will have fluoxetine discontinued at the end of 6 months. IPT therapists and fluoxetine-trained providers will be compensated per IPT/medication session/day completed, at the local currency equivalent of 10usd.

Fluoxetine treatment duration: Participants treated with fluoxetine will be tapered off fluoxetine at month 6.

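### The protocol contradicts itself on fluoxetine after month 6: the taper is stated without exception, yet fluoxetine non-remitters can be re-randomised at that point to IPT added to fluoxetine

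*Protocol*

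**What the plan says.** The protocol gives the end of fluoxetine treatment in several places, each time without a qualifier:

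- Fluoxetine treatment duration: "Participants treated with fluoxetine will be tapered off fluoxetine at month 6".
- IPT and fluoxetine treatment schedule and location: "At the month 6 visit, participants will be given instructions for tapering off fluoxetine, with decrease of the dose by 20mg" steps each week until zero. For the lowest dose: "Participants who were maintained on 20 mgs throughout the treatment period will have fluoxetine discontinued at the end of 6 months".
- Assessment schedule and rationale: at the end-of-treatment assessment, "fluoxetine recipients will be tapered off the medication".

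The second randomisation falls at the same point. Study Procedures gives first-line treatment as "12 weekly one-hour sessions of IPT (3 months) or 6 months of fluoxetine (tapering up to 60mg"), and says that those not in remission "at the conclusion of initial treatment will be re-randomized to second-line treatment". The sample size section confirms that first-line fluoxetine lasts 6 months.

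Study visits offers non-remitters a switch of treatment or "combination treatment (addition of IPT to fluoxetine or vice versa"). The sample size section counts switch to IPT and combination after fluoxetine as two separate arms of 242, within a second stage of 968.

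The SAP compares switch with combination by Fisher's exact test or an exact Wilcoxon rank-sum test. It does not say whether IPT-first and fluoxetine-first participants are pooled, and it plans no summary of second-line treatment received.

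**The concern.** A participant who has not remitted after 6 months of fluoxetine and is assigned to combination falls under two instructions. The taper text withdraws fluoxetine from month 6. The arm definition adds IPT to fluoxetine, which presupposes that fluoxetine continues. No legible text gives a second-line fluoxetine dose, schedule or duration that would decide between them.

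This matters because the protocol says it is powered for switch versus combination, the smallest difference it expects among its adaptive strategies. Within the fluoxetine-first half, that contrast is IPT plus fluoxetine against IPT alone, which is the comparison that sets 242 per arm. A provider who followed the taper text would remove the difference between the two arms. A finding of no difference could then reflect delivery rather than the treatments, and the SAP has no output that would tell these apart. Hypotheses 1b (relapse after combination) and 3b (severity as a moderator of switch versus combination) also need the arms to differ.

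**Working it through.** **Timing.** Re-randomisation is at the conclusion of initial treatment, and first-line fluoxetine lasts 6 months. For fluoxetine-first participants this places it at month 6, the visit at which the taper is ordered. The date is inferred from these two statements; the protocol does not state it in one sentence.

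**The two fluoxetine-first arms side by side**

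| Arm | By its definition | If the taper text is applied literally |
|---|---|---|
| Switch to IPT | IPT, fluoxetine stopped | IPT, fluoxetine withdrawn from month 6 |
| Combination after fluoxetine | IPT, fluoxetine continued | IPT, fluoxetine withdrawn from month 6 |

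**Length of the taper.** From 60 mg in weekly 20 mg steps there are three steps to zero. If the first step is taken at the visit, about 2 further weeks on drug remain; if it is taken a week later, about 3. From 40 mg it is about 1 to 2 weeks. Those on 20 mg throughout stop at month 6. First-line IPT is 12 weekly sessions; the same length is assumed for second-line IPT.

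**The plan's own sample size.** Inputs from the sample size section: d = 0.31 (combination versus medication alone); odds ratio 1.59 (combination versus psychotherapy alone, the trailing 28 read as a citation number); two-sided alpha 0.05; power 0.80. The formula is n per arm = 2(1.96 + 0.84)² / d².

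- d = 0.31 gives 164 (stated 164).
- d = ln(1.59) × √3/π = 0.2557 gives 241; the t-based solution is 241.1, which rounds up to 242 (stated 242). The rounded d of 0.25 would give 252.
- 4 × 242 = 968, and 968/0.5 = 1936, as stated.

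**Fluoxetine-first comparison alone, 242 versus 242.** As planned, the expected z is 0.2557 × √(242/2) = 2.81, so power is 80%. If both arms receive IPT with fluoxetine withdrawn, the true difference is near zero and a two-sided 5% test rejects about 5% of the time. The share affected is 2 × 242 = 484 of 968.

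**Pooled comparison, 484 versus 484.** Pooling, the equal split, and zero effect in the fluoxetine-first half are all assumptions. On the d scale, z = d × √(484/2).

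| Effect assumed | Intact in both halves | Lost in fluoxetine-first half |
|---|---|---|
| d = 0.25 in each half | z = 3.89, power 97% | mean d 0.125, z = 1.94, power 49% |
| d = 0.2557 in each half | z = 3.98, power 98% | mean d 0.128, z = 1.99, power 51% |
| d = 0.31 IPT-first, 0.25 fluoxetine-first | mean d 0.28, z = 4.36, power 99% | mean d 0.155, z = 2.41, power 67% |
| OR 1.59, 50% remission on switch (assumed) | 0.500 v 0.614, z = 3.59, power 95% | OR √1.59 = 1.26; 0.500 v 0.558, z = 1.80, power 44% |

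For the last cell, SE = √((0.250 + 0.247)/484) = 0.032 and 0.058/0.032 ≈ 1.80. The third row follows the plan's own effect sizes most closely, because IPT-first participants who switch go to fluoxetine alone, the contrast to which 0.31 applies.

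**The case against.** The strongest reply is that the taper text describes first-line treatment only. The schedule section sets out one course, from baseline through eight visits to month 6, and never mentions re-randomisation. The assessment paragraph that repeats the taper also leaves out re-randomisation and the month 9 visit, both of which the preceding paragraph gives. Applied to everyone by study month, the rule would also stop fluoxetine at month 6 in IPT non-remitters who began it around month 3, which is an unlikely intention. In addition, the design figure is not shown, and its legend separates branches that are treated further from those that only proceed to assessment.

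Most of this stands. A reader might infer that the plan makes the two fluoxetine-first arms the same treatment, so that half of the contrast compares a treatment with itself. The documents do not support that: they define the arms differently and count them separately. They merge only if the general duration sentence overrides the specific arm definitions. A reader might also take a single figure, such as a drop from 95% to 44%, as the trial's loss of power. That too is unsupported, because it needs a pooled analysis that neither document specifies and a remission rate that neither gives.

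What remains is that no legible sentence limits the taper to first line. The Fidelity section makes the gap harder to dismiss: fluoxetine charts are audited for dosing, and treatment counts as adherent only if nothing deviates from protocol. With two incompatible instructions, a provider following either one could be scored as deviating.

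**Conclusion.** The point holds as an internal contradiction that should be resolved before the second-line comparison is interpreted. It affects the content of two of the four second-line arms, 484 of 968 planned participants, within the contrast that sets the sample size. It is not evidence that the arms were delivered identically.

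The size is conditional. If the taper was applied to every fluoxetine-first participant, the 242 versus 242 comparison has about a 5% chance of rejection instead of 80%. That figure needs no pooling assumption. If the analysis also pools the two halves, power falls from about 95–99% to about 44–67%, depending on scale and effect. If the taper was confined to participants not assigned to combination, there is no loss. Partial application would fall in between.

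**What to change.** Reconcile the taper statements in Assessment schedule and rationale, in the treatment schedule section and under Fluoxetine treatment duration with the second-line arms in Study Procedures, Study visits and the sample size section. State to which participants the month 6 taper applies, and whether month 6 counts from enrolment or from the start of fluoxetine. If the design figure already answers this, put the answer in the text. Which clinical rule applies is for the investigators to decide.

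In the SAP, add a table of treatment actually received in each second-line arm (fluoxetine exposure and IPT sessions after re-randomisation), so that a null switch-versus-combination result can be interpreted. State also whether the comparison is made within each first-line group or pooled. The SAP is written in the past tense; if second-line treatment is already complete, the table can still be built wherever dosing records exist, and it then matters more.

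The cost is a protocol clarification, a note to providers, one extra table and one sentence on pooling. No additional participants are needed.

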Objectives: We propose to partner with local and national mental health stakeholders in Kenya to evaluate: (1) non-specialist delivery of evidence-based depression and/or PTSD treatment integrated within existing healthcare centers and by telephone in regard to clinical effectiveness and implementation parameters; including (2) costs and cost-benefit ratios for depression and/or PTSD care. Given that evidence-based psychotherapy and second-generation antidepressants are the two leading first-line treatments for depression and/or PTSD and are feasible to deliver in Kenya, our goal is to test an implementation strategy for improving equitable access to these treatments by integrating them with primary care.

Methodology:

Given the novelty of non-specialist depression care and primary care integration for Kenya, we will use an effectiveness-implementation hybrid design type I, which emphasizes effectiveness outcomes for the new setting and study population, while also gathering implementation data for future scale up. In collaboration with the 80-member FACES team currently providing integrated HIV care to Kisumu County Hospital (KCH) primary care outpatient clinics (~10,000 patients/month), we will randomize 2000 adult KCH and other Kisumu County Ministry of Health primary care patients with Major Depressive Disorder (MDD) to receive IPT delivered in person or by telephone by non-specialists trained in the study or fluoxetine delivered by fluoxetine trained providers in the study and follow them for 30 months. We will use the Exploration, Preparation, Implementation and Sustainment (EPIS) framework to inform the research and incorporate positive findings into practice. Given the high prevalence of MDD-PTSD co- morbidity, we will leverage the R01 to support a Sequential, Multiple Assignment Randomized Trial (SMART) by recruiting an additional 710 participants with MDD and/or PTSD (irrespective of HIV status) for a

total of 2710 participants. Local non-specialists will be trained in mental health care for the SMART and hired through the Kenyan Ministry of Health to work at KCH and other Kisumu County Ministry of Health facilities. After the study, Kisumu County will continue their payroll and the fluoxetine supply.

Data analysis: the study will compare short and long term (relapse) outcomes for IPT versus fluoxetine treatment (Aim 1), and calculate costs and cost-benefit ratios for each treatment arm (Aim 2).

Results:

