Retention: Based on previous work, retention is not expected to be a problem. Our pilot study of IPT for Sudanese refugees in Cairo had a 93% retention rate; our study of IPT for survivors of the Sichuan earthquake had an 85% retention rate and our ongoing study of integrated IPT care with HIV+GBV+ women in Kisumu has 300 enrollees with 20 dropouts (93% retention, to date). However, given uncertainty regarding generalizability to the KCH and other Kisumu County Ministry of Health facilities adult primary care clinics, the more conservative estimate of 20% drop-out will be used. However, provision of treatment over the telephone may improve retention rates. As part of retention efforts, participants will be asked to provide the name and phone number of a trusted adult who can be contacted if the study has concerns about participants' welfare or whereabouts. Therapists and fluoxetine providers will be asked to provide study cell phone numbers to study participants. Missed appointments will be followed with at least two efforts to reach the participant directly and/or through their contact (80% cell phone coverage). Likewise, at least two efforts will be made to reach drop-out participants for remaining measures.

Acute mental health care: IPT therapist and fluoxetine training will include risk assessment and referral procedures for acute mental health care needs. See Protection of Human Subjects section for details.

Clinical evaluators: Clinical evaluators will be blind to treatment group and will conduct baseline screening at the primary care clinic prior to initiating treatment, as well as re-assessments at months 1.5 (mid-treatment for IPT), 3 (mid-treatment for fluoxetine), 6, 9 month 12, 18, 24 and 30. Candidate clinical evaluators will undergo a two day training during which they will be introduced to the study measures and their proper application. At the conclusion of the training, the candidates will be observed in their administration of the measures, assessing for accuracy and completeness. If successful, they will be evaluated for reliability by conducting a group interview and comparing measure results. Those who demonstrate both accuracy and inter-rater reliability will be invited to join the study. Monetary compensation will be provided for completed measures at the local currency equivalent of 7usd.

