Cost-benefit analyses. An important question for policymakers concerns the economic returns to investments in treating and improving mental health. We will use data obtained on the economic status of those treated to calculate the economic benefits associated with treated mental health disorders (both pooled analyses of IPT or fluoxetine treatment and separate analyses of IPT and fluoxetine treatment). We will also incorporate data on health care utilization and hospitalizations (Table 1). The value of these economic benefits will be summarized on a per-person basis and then combined with the implementation cost data to generate a rate of return on mental health expenditures (in general and by treatment type –IPT or fluoxetine). This rate of return is net gains in all economic measures divided by implementation costs, x 100 to yield % return. Cost and income measures will be adjusted for inflation and discounting during the 3 year study period.

Human participants in the project

Target population. Adult primary care outpatient clinic attendees at Kisumu County Hospital (KCH) and other Kisumu County Ministry of Health facilities.

Sample size calculations: SMART designs are used to inform the construction of optimal Adaptive Treatment Strategies (ATS), which is our goal. Therefore, we will power our study to detect the smallest difference between the various ATS included in the study design. The proposed SMART examines (1) first line treatment strategies with IPT or fluoxetine, including long-term relapse risk for participants who remit with initial treatment and (2) second line treatment strategies for non-remitters—specifically, treatment “switch” (from IPT to fluoxetine or vice versa) versus treatment “combination” (addition of IPT to fluoxetine or vice versa). Based on the current evidence base, we

expect that differences between switching or combining treatment will be smaller than other ATS comparisons in the study and we will therefore power the study to detect this difference.

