As it pertains to antidepressants and psychotherapy, the evidence base comparing “switching” versus “combining” treatment for non-remitters (second line treatment) is still developing. However, the field does have meta-analytic data on the differences between treating depression with antidepressants or psychotherapy alone, versus their combination. A 2009 meta-analysis (n=2036) which compared combination treatment (psychotherapy and pharmacotherapy) to pharmacotherapy alone for depression found an effect size of 0.31 (Cohen’s d).²⁷ A 2007 meta-analysis (n=903) found that the remission rate for major depression treated with psychotherapy and pharmacotherapy was better than psychotherapy alone, with an odds ratio of 1.5928, which when converted to a Cohen’s d is 0.25.²⁹ While specific studies have not yet been completed for IPT and PTSD, we leveraged the above-referenced meta-analyses of the effects of general psychotherapy and general pharmacotherapy to estimate sample size for the proposed study. Based on those studies, we would need approximately 164 per treatment arm to compare combined psychotherapy-medication treatment with medication alone, and 242 to compare combined psychotherapy-medication with psychotherapy, alone (using a two-sided alpha of 0.05 and power of 0.80). Using the conservative estimate, we will need 242 for each of the four treatment arms (968, total) after the second randomization (switch to fluoxetine, switch to IPT, combination after fluoxetine, combination after IPT). Note, this strategy uses fluoxetine treatment for 6 months as a first line treatment,

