consistent with the original R01 submission and responsive to reviewers' comments (summary statement response) on our funded U01 (DAPPER) study. While effectiveness data on treatment of depression in HICs (STAR*D) indicate that only approximately one-third remit with first line treatment, preliminary data from our current IPT study in Kisumu indicate remission rates over two-thirds. We will use a conservative estimate of the numbers entering the second randomization phase (non-remitters) and assume that half of study participants will need second-line treatment. Based on that estimate, the 968 participants randomized to the second stage of the SMART should represent 50% of those enrolled at the start of the trial, or 1936. Allowing for a 40% drop out rate across the 33 month duration of the study (domestic migration is common in Kenya³⁰), we will need 2710 participants for the SMART.

The additional number required for integration of the SMART design is 710 participants. Making a conservative assumption of ~20% prevalence of MDD and/or PTSD among primary care patients, we will screen 3,550 individuals to enroll 710 participants. While KCH and other Kisumu County Ministry of Health facilities see over 10,000 adult primary care patients per month, we will assume that only 20% of clinic attendees will undergo screening, and we will budget 3 months for recruitment. In order to avoid overwhelming mental health care providers, these 3 months of recruitment will be dispersed across a 18 month period: enrollment will halt when providers' caseloads are full and resume when at least 20% availability is regained. We will also work with Community Health Workers (CHWs) and Community Health Volunteers (CHVs) to

mobilize and sensitize the community about mental health services and refer community members to one of the health facilities for screening for the SMART-DAPPER study.

Eligibility criteria

Inclusion criteria:

- (1) KCH and other Kisumu County Ministry of Health facilities adult primary care outpatient clinic attendees who meet the threshold criteria for DSM-V for MDD and/or PTSD. .
- (3) Ability to attend weekly IPT sessions/fluoxetine monitoring in person or by telephone;
- (4) 18 years or older.

Exclusion criteria:

- (1) Cognitive dysfunction compromising ability to participate in IPT or accurately take fluoxetine (lack of orientation to person, place, time and situation);

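### The Retention section plans on 20% drop-out and the sample size on 40%, never reconciled; 2710 comes from the 40% but absorbs only 28.6% loss, so at 40% it gives about 203 per second-stage arm and 73% power, not 242 and 80%

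*Protocol*

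**What the plan says.** **Protocol, Retention.** After citing retention of 93%, 85% and 93% in the team's own studies, the section says that "the more conservative estimate of 20% drop-out will be used". It gives no period for the 20% and does not say which calculation will use it.

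**Protocol, Sample size calculations.** The trial is sized on second-line switch versus combination, because "we expect that differences between switching or combining treatment will be smaller than other ATS comparisons in the study". At two-sided alpha 0.05 and power 0.80, "we will need 242 for each of the four treatment arms", 968 in all. With half of participants assumed to need second-line treatment, this becomes 1936 enrolled. The last step reads "Allowing for a 40% drop out rate across the 33 month duration of the study", justified by domestic migration, and ends with "we will need 2710 participants for the SMART".

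**Protocol, follow-up.** The abstract says the study will "follow them for 30 months". Study visits has assessments "at six month intervals until month 30", and Assessment schedule and rationale has participants "monitored at 6-month intervals until month 30".

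**SAP.** It names the tests for the re-randomized comparison (Fisher's exact, exact Wilcoxon rank-sum) but no time point and no loss assumption.

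**The concern.** Two sections of one protocol give different planning figures for drop-out, one half the other, and neither refers to the other. The section that sets the enrolment target also uses a duration three months longer than the follow-up described everywhere else.

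The loss rate determines how many participants reach the second-stage analysis, which is the contrast the trial is sized on. If the 40% is meant literally, the stated 242 per arm and 80% power should survive a 40% loss from 2710. If they do not, the plan claims a power that its own assumptions do not deliver, and a null switch-versus-combination result would be read with more confidence than it deserves.

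**Working it through.** **Inputs** (Protocol, Sample size calculations, unless noted)
- Effect sizes: d = 0.31 (combination versus medication alone); odds ratio 1.59, given as d = 0.25 (combination versus psychotherapy alone). The digits after 1.59 in the text are read as a citation number.
- Two-sided alpha 0.05, power 0.80; 242 per arm, four arms; 50% non-remission.
- Loss: 40% (Sample size calculations); 20% (Retention).

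**Step 1. Reproduce the plan's figures.**
- Per arm, n = 2(1.960 + 0.842)² / d². For d = 0.31 this gives 164, as stated.
- Converting the odds ratio: d = ln(1.59) x √3/π = 0.2557. This gives 241 by the normal approximation and 242 with the t-test, as stated. The rounded d = 0.25 would give 252.
- 4 x 242 = 968, and 968 / 0.50 = 1936, as stated.

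**Step 2. Find which loss figure yields 2710.**

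| Loss | 1936 x (1 + loss) | 1936 / (1 − loss) |
|---|---|---|
| 20% | 2323 | 2420 |
| 40% | **2710** | 3227 |

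Only 40%, applied as a multiplier of 1.4, gives 2710. The 20% figure does not enter.

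**Step 3. Find how much loss 2710 absorbs.** 1 − 1936/2710 = 0.286. So 242 per arm remain only if loss is at most 28.6%, a rate that appears in neither document. On d = 0.25 the need is 8 x 252 = 2016 participants, and the limit is 1 − 2016/2710 = 25.6%.

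**Step 4. Per-arm number and power with 2710 enrolled.** The number per arm is 2710 x (1 − loss) x 0.5 / 4. Power is Φ(d√(n/2) − 1.96).

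| Loss | Remaining | Per arm | Power, d = 0.2557 | Power, d = 0.25 |
|---|---|---|---|---|
| 20% | 2168 | 271 | 84% | 83% |
| 28.6% | 1935 | 242 | 80% | 78% |
| 40% | 1626 | 203 | 73% | 71% |

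For example, at 40% loss: 0.2557 x √(203.25/2) − 1.96 = 0.617, and Φ(0.617) = 0.73.

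**Step 5. Effect of 33 versus 30 months.** If loss accrued at a constant rate (an assumption) and reached 40% at month 33, it would be 1 − 0.6^(30/33) = 37% at month 30. The discrepancy is real, but its numerical effect is small.

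**The case against.** **A reader might infer that 2710 rests on no consistent loss figure.** The documents do not support that. The total follows reproducibly from the 40% alone, and the Retention figure plays no part in it.

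**A reader might also infer that the conflict between 20% and 40% causes the power shortfall.** It does not. The shortfall arises because the allowance was applied by multiplying by 1.4 instead of dividing by 0.6. If 20% is the right loss, 2710 gives more than 80% power.

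**The two rates may describe different periods.** The 20% follows retention rates from earlier studies of interpersonal psychotherapy (IPT), and the Feasibility section sets a benchmark of under 20% leaving during treatment. The 40% is expressly for the whole study. Both could be true. But the Retention section gives no period, the Feasibility figure is a success criterion and not a planning rate, and no text links the two.

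**The 33 months may be deliberate.** Study duration need not equal follow-up per participant, and the same section budgets 3 months of recruitment, so 30 + 3 is possible. But that section spreads those 3 months over 18, and does not derive the 33. The text therefore needs correction or explanation, and the documents do not settle which.

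**Whole-study loss is conservative for an earlier contrast.** This has force. It is tempting to fix the second-line endpoint at month 9, by adding the second treatment's course to the first-line duration. At a constant rate, loss by then would be about 13% (9% at month 6, 17% at month 12), leaving about 295 per arm and 87% power. But neither document names a time point for the contrast. Month 9 is an inference, and the 13% rests on the constant-rate assumption, so neither can be used to declare the trial adequately powered.

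**Conclusion.** The point holds as a defect in the stated planning figures. The protocol declares a 20% drop-out in one place and sizes on 40% in another without reconciling them, and it attaches the 40% to an unexplained 33-month duration. Under its own 40%, 2710 delivers about 203 per second-stage arm and 73% power (71% at d = 0.25). The stated 242 and 80% are met only if loss is at most 28.6%. At 20% loss the trial has 271 per arm and 84% power (83% at d = 0.25).

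It does not follow that the trial is underpowered. Whether it is depends on the loss at the second-line analysis, which the documents do not give.

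The figures assume 50% non-remission after each first-line treatment, equal allocation to the four second-stage arms, loss independent of remission, and the protocol's own sizing basis (a standardized difference, two groups, two-sided 0.05). They are not power figures for Fisher's exact test.

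**What to change.** 1. In Sample size calculations, state the loss rate that applies to switch versus combination, and the time point at which that contrast is analysed. Name the same time point in the SAP.
2. State separately the expected loss over the whole study, for the relapse and month-30 analyses.
3. Give the 20% in Retention a period and a use, so that it agrees with the sample size section.
4. Correct the 33 months to match follow-up, or explain it.
5. Restate the per-arm number and power that 2710 delivers under the chosen loss, using 2710 x (1 − loss). If 40% is kept, these are about 203 and 73%. The 80% may stand only if the stated loss is at most 28.6% (25.6% on d = 0.25).

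The cost is wording and restated figures, with no new data and no change to the analysis. Restating does not itself change enrolment. If both the 40% and the 80% power were to be kept, the total would be 1936 / 0.6 = 3227, which is 517 more than planned.
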